#### 7.5 Serious Adverse Event Reporting

For serious adverse events from patients using an AbbVie product, the physician will notify the AbbVie contact person identified below within 24 hours of the physician becoming aware of the event.

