# 5.2 Secondary Objectives:

- i. To compare the real life effectiveness of adalimumab to topical and traditional systemic agents in the prevention of development of articular and extra-articular manifestations in patients with moderate to severe Plaque PS.
- ii. To describe the profile and regional variation in terms of demographics, disease parameters, flare up trigger, comorbidities and concomitant medication use of Canadian patients with moderate to severe Plaque PS.
- iii. To describe the current practices and regional variation among Canadian dermatologists with respect to the screening and detection of articular manifestations indicating onset of PsA in patients with moderate to severe Plaque PS.

- iv. To describe the incidence of and risk factors for the development of articular and extra-articular manifestations in Canadian patients with moderate to severe Plaque PS.
- v. To describe the current population based burden of illness incorporating Health Care Utilization, Health Care Costs, Quality of Life, Psychological impact Work Productivity of moderate to severe Plaque PS in Canada.
- vi. To assess the impact of topical agents, traditional systemic agents and adalimumab on the Plaque PS related burden of illness incorporating Health Care Utilization, Health Care Costs, Quality of Life, Psychological impactWork Productivity in Canada.
- vii. To provide an ongoing assessment of the safety and tolerability of adalimumab, systemic and topical agents used in the management of moderate to severe Plaque PS in Canada.

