#### 7.4 Serious Adverse Event Collection Period

Serious adverse events will be reported to AbbVie from the time the physician obtains the patient's authorization to use and disclose information (or the patient's informed consent) until 30 days or 5 half-lives following the intake of the last dose of physician-prescribed treatment.

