At the conclusion of the study, the completed signed and dated case report forms for the enrolled patients should be provided to the study data management center by the investigator for every patient enrolled in the study. Electronic signatures will be used in the case of an EDC system. A distinct case report form should be created for each unique instance when data is to be collected. ONLY data specified in the protocol should be collected and submitted to the study data management center. The investigator or staff under his/her supervision must complete the case report forms and neither AbbVie nor any agents acting on behalf of AbbVie may complete the case report forms.

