In order to better assess the impact of the treatment received and changes in the regimen the treatment will be handled as a time – dependent covariate in these analyses.

With respect to achieving therapeutic response end points and incidence of articular and extra-articular manifestations between group differences will be assessed with multivariate logistic regression while Cox proportional hazard models will be used to assess between group differences with respect to the time of achieving therapeutic response and first occurrence of articular and extra-articular manifestations.

Descriptive statistics will be used to assess the between group and regional differences with respect to patient characteristics and disease parameters. Descriptive statistics will also be used to assess the practice patterns of Canadian dermatologists in the management of patients with moderate to severe PLAQUE PS. The study cohorts will be divided into Canadian regions as Quebec, Ontario, Maritimes and Western Canada.

Underdiagnosis of articular and extra articular manifestations will be assessed by the prevalence of existing articular manifestations and a survey of participating physicians with respect to their estimates of the prevalence of articular and extra- articular manifestations in the patients.

Safety will be assessed by the incidence of treatment emergent adverse events with adjusted relative risks used to compare the three treatment groups.

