### 2.10.2 Safety Measures

Safety and tolerability will be assessed with the incidence of treatment-emergent adverse events. Incidence of treatment emergent serious adverse events will be recorded by the treating physician through the 24 months of treatment. Severity of the adverse event and causal relation to the treatment will be assessed by the treating physician. All adverse events will be coded as per the MedDRA dictionary of terms.

i. All serious adverse events will be recorded and reported as per regional regulatory guidelines and requirements.

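### Protocol 7.4 and 7.5 conflict on whose serious adverse events go to the sponsor, and no common recording route is shown, so the planned three-group safety relative risks are open to unequal ascertainment

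*Protocol*

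**What the plan says.** **Scope of collection.** Protocol 7.4 sets the start as "Serious adverse events will be reported to AbbVie from the time the physician obtains the patient's authorization to use and disclose information" and the end as "until 30 days or 5 half-lives following the intake of the last dose of physician-prescribed treatment". It has no product limit, and its end point is tied to whatever the physician prescribed. Protocol 7.0 requires spontaneously reported SAEs to be reported, also without a product limit. SAP 2.10.2 says: "All serious adverse events will be recorded and reported as per regional regulatory guidelines and requirements".

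**Procedure.** Protocol 7.5 states who notifies whom and by when, but only for one class of patient: "For serious adverse events from patients using an AbbVie product, the physician will notify the AbbVie contact person identified below within 24 hours".

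**Forms.** Protocol 9.0 lists four CRF parts: baseline, follow-up visits, additional visits and end of study. It also states: "ONLY data specified in the protocol should be collected and submitted to the study data management center". Table 1 in the Protocol and its counterpart in SAP 2.6 have no adverse event or SAE row.

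**Use of the data.** Secondary objective vii in Protocol 5.2 is "To provide an ongoing assessment of the safety and tolerability of adalimumab, systemic and topical agents". The comparison itself comes from Protocol 10.2: "Safety will be assessed by the incidence of treatment emergent adverse events with adjusted relative risks used to compare the three treatment groups".

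**The concern.** A relative risk between treatment groups is interpretable only if events are found and recorded equally well in each group. Here the one visible SAE instruction with an actor, a recipient and a deadline depends on the exposure being compared. Adalimumab is the only AbbVie product that the documents name as a study treatment, and half of the planned 660 patients (165 + 165) start on something else. A site with a hospitalised methotrexate patient would find that 7.4 says to report and that 7.5 gives a procedure only for someone else.

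If sites resolve that conflict in favour of 7.5, comparator events are missed more often. This would be differential outcome misclassification. The covariate models, propensity scores and stratification in SAP 3.2 address baseline imbalance between groups and do nothing about unequal reporting. Protocol 7.0 asks only for spontaneously reported SAEs, so no active questioning evens things out.

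**Working it through.** The plan states no SAE rate, expected count or capture rate, so there is no figure to reproduce. The check has two parts.

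**1. The rules side by side**

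| Place | Limited to AbbVie product? | What it supplies |
|---|---|---|
| Protocol 7.0 | No | Duty to report spontaneously reported SAEs |
| Protocol 7.2, 7.3 | No | Severity and relationship ratings for all SAEs |
| Protocol 7.4 | No | Recipient (AbbVie) and collection period |
| Protocol 7.5 | Yes | Actor, contact and 24-hour limit |
| SAP 2.10.2 | No | Recording by the physician over 24 months |
| Protocol 9.0; Table 1 (both documents) | – | No SAE page or row shown |

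The duty is general and the procedure is restricted. Nothing visible states how a comparator SAE reaches the database with the ratings that 7.2 and 7.3 require. The relationship definitions in 7.3 refer to the study drug, a term not defined for each cohort.

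**2. What unequal capture would do**

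Let capture be the share of true SAEs that reach the database. Then:

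apparent RR = true RR × (capture on adalimumab ÷ capture in comparators)

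With a true RR of 1 and an assumed 90% capture on adalimumab:

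- comparator capture 90%: 0.90 ÷ 0.90 = 1.0
- comparator capture 50%: 0.90 ÷ 0.50 = 1.8
- comparator capture 25%: 0.90 ÷ 0.25 = 3.6

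These ratios do not depend on the true risk. To show counts, take the planned 330:165:165 from Protocol 10.3, pool the comparators to 330, and assume that 5% of patients truly have an SAE:

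- each side, true: 330 × 0.05 = 16.5
- adalimumab, recorded: 16.5 × 0.90 = 14.9
- comparators, recorded: 16.5 × 0.50 = 8.3, or 16.5 × 0.25 = 4.1

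The chance of a falsely significant difference follows from the usual normal approximation for two proportions, two-sided 5%, 330 per side, with full capture on adalimumab. Worked case, 5% true risk and 50% comparator capture:

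- recorded risks: 0.05 and 0.025, difference 0.025, pooled risk 0.0375
- null standard error: √(2 × 0.0375 × 0.9625 ÷ 330) = 0.01479
- alternative standard error: √((0.05 × 0.95 + 0.025 × 0.975) ÷ 330) = 0.01476
- z = (0.025 − 1.96 × 0.01479) ÷ 0.01476 = −0.27, so the chance is about 39%

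The same calculation over a range of assumptions:

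| Assumed true risk | Capture 75% (RR 1.33) | Capture 50% (RR 2.0) | Capture 25% (RR 4.0) |
|---|---|---|---|
| 3% | 9% | 25% | 57% |
| 5% | 12% | 39% | 79% |
| 10% | 21% | 69% | 98% |

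All risks and capture rates here are assumptions. The calculation pools the comparators and is unadjusted, whereas Protocol 10.2 plans adjusted comparisons of three groups.

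**The case against.** The best case for the plan is that 7.5 is an expedited-notification rule, not the collection rule. Protocol 7.0 and 7.4 and SAP 2.10.2 cover SAEs in every cohort, and 7.2 and 7.3 have all of them rated. Protocol 6.5 asks that everything about patient management over 24 months be recorded, expressly to avoid bias. Protocol 6.5.1 has important changes in history and examination recorded at follow-up. Protocol 8.0 has site staff trained in adverse event reporting. The limit in 9.0 to protocol-specified data does not shut SAEs out, because section 7 specifies them. The 9.0 list is by visit and need not name every page. The contact text that followed the quoted sentence in 7.5 is not in the public version and may say more.

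Most of this stands, and it rules out several stronger readings that a reader might infer:

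- *Comparator SAEs are under-collected by rule, or sites have no duty to report them.* Protocol 7.0 and 7.4 state the duty without a product limit.
- *A topical patient who switches to adalimumab becomes reportable only from the switch.* Protocol 7.4 starts at consent; only the 24-hour procedure in 7.5 depends on product use.
- *The relative risk is biased.* If sites follow 7.0, 7.4 and SAP 2.10.2 equally in all cohorts, capture is equal and no distortion arises.
- *Objective vii itself compares cohorts.* It calls for an assessment. The comparison is in Protocol 10.2 and concerns treatment-emergent adverse events generally. SAP section 3 sets out no comparative safety model.

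What the objection does not answer is the conflict between 7.4 and 7.5, or the lack of a visible common form. An SAE that surfaces as a change in medical history may arrive without the ratings required in 7.2 and 7.3. A comparator rule in the unseen part of 7.5 would help only if it also brought those events into the study data.

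**Conclusion.** The point holds as a conflict between two rules that puts a planned analysis at risk. It does not show that bias has occurred. The general duty in 7.4 and the product-limited procedure in 7.5 cannot both guide a site with a comparator SAE, and no form shown settles the matter. If the conflict lowers comparator capture, the error runs in one direction, raising the relative risk for adalimumab, and the planned adjustment cannot correct it.

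The size cannot be derived from the documents. The apparent relative risks of 1.8 and 3.6 rest on a true value of 1, assumed capture of 90% on adalimumab, and assumed capture of 50% or 25% in the comparators. With equal capture the figure stays at 1. Safety is a secondary objective, so the primary PGA comparison is unaffected.

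**What to change.** 1. Reconcile 7.4 and 7.5. State that an SAE in any enrolled patient, whatever the psoriasis treatment at onset, is recorded in the study database by the same procedure. If a separate 24-hour notice for AbbVie products is kept, describe it as additional to that common duty.
2. Add an SAE page to the CRF parts in Protocol 9.0, with onset date, psoriasis treatment at onset, seriousness criterion, severity and relationship. Treatment at onset is needed because patients may switch cohorts and treatment is to be handled as time-dependent.
3. Add an SAE row to Table 1 in the Protocol and in SAP 2.6.
4. If comparator SAEs will not be captured equally, delete the three-group relative risk from Protocol 10.2 and report safety descriptively by group. Objective vii can then stand as written.

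A site query when the Health Care Utilization Questionnaire shows a hospitalisation without a matching SAE page is optional and only a partial safeguard. The questionnaire asks about psoriasis-related hospitalisations and is scheduled only at months 0, 6, 12 and 24, so it would miss admissions for other causes.

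The cost is a short text change, one CRF page, one table row and a modest extra reporting load at sites for comparator SAEs. Events that were never captured are hard to recover after database close.

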## 7.6 Pregnancy Reporting

In the event of pregnancy, the physician will notify by telephone only the AbbVie contact identified in Section 7.5 within 24 hours of the physician becoming aware of the pregnancy.

## 7.7 Unusual Failure in Efficacy

Lack of efficacy is the failure of health product to produce the expected intended benefit. The Canadian Food and Drug Act and Regulations require that manufacturers report cases of unusual failure in efficacy to Health Canada for new drugs in the post-marketing setting, including in Phase IV studies.

Physicians should exercise clinical judgment to determine if the lack of efficacy is related to the drug itself, rather than one of treatment selection or disease progression since health products cannot be expected to be effective in 100% of the subjects.

The Investigator shall report all cases of unusual failure in efficacy coincident with the use of the study drug to AbbVie within 24 hours by telephone at or by email at . When calling this number, the Investigator will identify himself as an Investigator of the study reporting an unusual failure in efficacy to Medical Information. If there is any need to fax information, the Investigator will use the following fax number: Fax:

## 8.0 Ethics and Quality

The study will be submitted for review and approval at a central ethics committee, local ethics review boards, as required for individual sites and the College of Physicians and

Surgeons of Alberta. The boards will review the study protocol, informed consent and patient questionnaires. A list of participating physicians will be provided to the review boards. No study activities will be undertaken prior to obtaining the relevant approval of the Independent Ethics Review Boards.

Prior to being enrolled in the study and the conduct of any study assessments, written informed consent will be obtained from the patient or designated legal representative. The investigator will explain the study to the patient along with the requirements for completion of the self administered questionnaires. The informed consent will provide permission for the patient's data to be used **anonymously** in the study. In addition, written authorization will be provided by the patient to authorize contact by the study personnel at specified coordinates.

Patient confidentiality will be protected at all times by using a randomly generated patient study identification number that will identify each unique patient. The name, address, telephone numbers, provincial insurance numbers, hospital record numbers or any other identifier will **NEVER** be entered in any page of the Case Report Form, questionnaire or return envelope. The link between patient contact information and the patient study identification number will be kept in a secure location and password protected computer folder that is separated from other information and is accessed only by authorized study personnel.

Prior to being included in the study all sites will be assessed for compliance with local requirements for the practice of medicine including validation of the physician's license and specialization certificates. In addition, all site personnel will be educated with respect to Good Clinical Practices (GCP) and the requirements for data reporting and in particular adverse event reporting of the study. Sites with experience in the conduct of clinical research will be preferred.

Data quality will be ensured by conducting a study audit, random sample monitoring,

logic edit checks and statistical assessments. An audit of 100% of the sites will be conducted to ensure that the patients entered in the study fulfill the inclusion and exclusion criteria.

Monitoring with source document verification when possible will be conducted on a maximum random 10% sample of the sites.

Edit checks will be programmed in the data management system by Cato Research. The edit checks identify out of range and illogical entries. Edit checks generate queries that are reviewed by the project manager who will either proceed with a level I correction or will issue a data clarification request to the site. Level I corrections are those that could be decided by the project manager or the project scientific director without requiring contact with the site. *Typical example of level I corrections is the year of the study visit date.* The criteria for level I corrections will be described in the data management plan. In addition a listing of all level I corrections will be transmitted to the study sites at regular intervals for confirmation.

Statistical methods employed to identify out of range or outlying datapoints will include frequency distributions, box plots and contingency tables. Statistical analyses to identify these issues will be conducted on a regular basis as part of the data management process. Patient records with potential errors will be flagged and queries will be generated that will be reviewed by the project manager who will determine whether a data clarification request should be transmitted to the site.

All data clarification requests will be transmitted to the sites by fax or by email depending on the preference of the site investigator. Corrections will be entered into the database depending on the response from the site. A patient record will be considered close when there are no pending data clarifications.

Data management for the current study will be conducted on Cato Research system The

data management procedures and computer systems used by Cato Research have been subjected to regular validation and verification. The data management system developed for the current study will be subjected to a study specific audit. In addition, the study will be audited by the Director of Quality Assurance for compliance with the company and study specific standard operating procedures. Compliance with GCP, 21 CRF Part 11 are assured through these processes and the Quality Assurance master Plan.

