Finally, continuous monitoring of the safety of adalimumab is essential in order to assess whether the safety profile in a real – life setting is comparable to that expected on the basis of the data reported in controlled clinical trials and to ensure detection of any emerging signal.

The current study will address the above questions by conducting a prospective observational study of Canadian patients with moderate to severe psoriasis for whom change of current treatment is indicated. Patients will enter the cohort at the time that their treatment is changed and therefore patients treated with topical agents, traditional systemic agents and adalimumab will be eligible to be included in the study. The rationale for limiting the anti-TNF alpha agent to adalimumab is based on the prevention of within class variation with respect to clinical decision making, response to treatment and incidence of adverse events.

Follow up will be for 24 months and assessments will be as per routine clinical care and according to the judgment of the treating physician. However, follow up visits at approximately 3, 6, 12, 18 and 24 months will be recommended.

There will be a total of 660 patients with psoriasis enrolled from the clinics of 30 - 40 Canadian community dermatologists. The sample of clinicians will be a random proportional representation of the distribution of dermatologists and patients in Canada, thus allowing valid generalization to the Canadian population of psoriasis patients. In addition, enrollment of the patients in the study will be on the basis of change in current treatment due to lack of response or tolerability. The decision to change treatment must be reached prior to enrollment in and independently of the current study.

The study will assess clinical and patient reported outcomes that are relevant in the management of psoriasis and its impact on the patient's quality of life and societal burden

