# 6.0 Investigational Plan

This is a Canadian Post Marketing Observational Study utilizing a prospective cohort design. Patients are entered into the study cohort at the time of change of their Psoriasis treatment for any reason and are followed for a maximum of 24 months with recommended assessments at 3, 6, 12, 18 and 24 months after baseline. Treatment of the patients and follow up will be according to the physician's judgment, regional regulations and the product monograph. Off-label use will not be permitted and these patients will not be included in the study. Dose changes including escalation will be allowed as per the physician's judgment for patients that were treated as per indication when they were enrolled in the study.

There will be 660 patients enrolled from the practices of approximately 30 - 40 dermatologists across Canada. The study sample will be randomly selected and proportional to the Canadian population and distribution of dermatologists in Canada.

The following patient cohorts will be defined:

i. Initiated treatment with a new topical agent that was not used before or already on treatment with a topical agent and not responding requiring a change of treatment

type, frequency or dose.

- ii. Initiated treatment with a new systemic agent that was not used before alone or in combination with topical agents.
- iii. Initiated on treatment with adalimumab alone or in combination with topical agents.

In the case that the patient is switched from one cohort to another during the course of the study, follow up will continue as per the study protocol. For these cases, the treatment will be considered as a time dependent variable in the assessment of the study outcomes. In addition, depending on the number of patients switching cohorts, separate cohorts may be defined to include those patients that change treatment during the study.

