## 6.3 Investigator Selection Criteria

- i. A random sample of 30-40 dermatologists will participate in the study.
  - a. Physicians participating in the study must have experience in the conduct of clinical research and in particular good clinical practices (GCP) or must be willing to be trained in GCP.

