### 2.8 Patient Selection

Patients will be enrolled from the offices of community rheumatologists across Canada treating patients with PS. The sample of physicians invited to participate in the study will be selected in a way that it is a random representative sample of the Canadian population and distribution of dermatologists.

All patients with PS treated at the participating centers will be potentially eligible to be included in the study. Those fulfilling the study inclusion and exclusion criteria will be invited to participate in the study by the site investigator or designee. Treatment will be according to the treating physician's judgment and routine care and must adhere to the product monograph and regional regulatory requirements. Use of medications for the management of PS that is off – label or not in accordance with existing regulations will not be permitted. Prior to inclusion in the study all patients will be required to sign a written informed consent agreeing to allow use of their data in the study. Since this is not an interventional study and patients are treated as per routine care the purpose of the informed consent will be to allow the use of the data and contact of the patients by the study personnel as required. The study protocol, informed consent, questionnaires and participating physicians will be approved by a central or local independent ethics review board as required by regional or institutional regulations.

COMPLETE - PS Statistical Analysis Plan Version 3.0 July 23rd, 2015 Page 18 of 231

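### Protocol 8.0 prefers research-experienced sites while the Protocol and SAP call the sample random, so the stated basis for generalising the descriptive results to Canada does not hold as written

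*Protocol*

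**What the plan says.** Protocol 4.0 states that "The sample of clinicians will be a random proportional representation of the distribution of dermatologists and patients in Canada" and draws the consequence in the same sentence: "thus allowing valid generalization to the Canadian population of psoriasis patients". Protocol 6.0 says "The study sample will be randomly selected and proportional to the Canadian population and distribution of dermatologists in Canada", and SAP 2.4 repeats it. Protocol 6.1 and SAP 2.8 say that the invited physicians are "selected in a way that it is a random representative sample of the Canadian population and distribution of dermatologists". Protocol 6.3 opens with "A random sample of 30-40 dermatologists will participate in the study".

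Two passages bring in research experience. Protocol 6.3 sets a condition for taking part: physicians "must have experience in the conduct of clinical research and in particular good clinical practices (GCP) or must be willing to be trained in GCP". Protocol 8.0, after describing licence checks and GCP education for all site personnel, adds: "Sites with experience in the conduct of clinical research will be preferred".

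**The concern.** Random selection is the only reason the Protocol gives for generalising to Canada. A preference makes a site's chance of selection depend on whether it has done research before. The sample is then no longer the unqualified random sample described elsewhere.

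Three secondary objectives are statements about Canada rather than comparisons between treatments: the profile of Canadian patients (ii), dermatologists' practice in screening for joint disease (iii), and the population-based burden of illness (v). For these, representativeness is what makes the estimate valid. Objective iii is the most exposed, because the physician is the unit described. Research-experienced dermatologists may differ from others in screening, referral or case mix. If so, the report would present a preference-selected group of practices as a random national sample.

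**Working it through.** The Protocol gives no figure to reproduce here. The check is a comparison of the passages, followed by an illustration with assumed inputs.

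**1. Eligibility and preference are different rules.** The condition in Protocol 6.3 admits any physician who has experience or will accept training. A random draw among eligible physicians would be compatible with it. The sentence in Protocol 8.0 ranks eligible sites, which an unqualified random draw does not do.

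**2. What could reconcile them.** A preference can sit inside a probability sample if selection probabilities are known and used in the analysis. That needs a sampling frame, a selection procedure, a rule for applying the preference, and weights or adjustment. Neither document describes any of these. SAP 3.11 analyses practice patterns with descriptive statistics. The propensity scores and covariate models in SAP 3.2 address how patients come to receive a treatment, not how sites come to be in the study.

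**3. Proportional allocation does not repair it.** Proportionality is tied to population and to where dermatologists practise. Experienced sites can be over-represented within every region while the regional counts stay proportional.

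**4. It could not be examined afterwards.** Neither Protocol Table 1 nor the CRF sections listed in Protocol 9.0 include site research experience.

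**5. Illustration (every input is assumed).** Let p be the experienced share of dermatologists nationally, s their share in the study, and e and o the proportion following some practice among experienced and other dermatologists. The error of an unweighted national proportion is

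error = (s − p) × (e − o).

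- *Central illustration:* p = 0.30, s = 0.80, e = 0.65, o = 0.45. The study would show 0.80 × 0.65 + 0.20 × 0.45 = 0.61. The national value is 0.30 × 0.65 + 0.70 × 0.45 = 0.51. The error is 10 percentage points.
- *How strong a preference this implies:* (0.80/0.20) / (0.30/0.70) = 9.3, so the odds of selection are about nine times higher for experienced sites.
- *Milder preferences:* with selection odds k, s = kp / (kp + 1 − p). For p = 0.20, k = 2 and e − o = 0.10, s = 0.333 and the error is 0.133 × 0.10 = 1.3 points. For p = 0.30, k = 5 and e − o = 0.30, s = 0.682 and the error is 0.382 × 0.30 = 11.5 points. Over p from 0.20 to 0.50, k from 2 to 5 and e − o from 0.10 to 0.30, the errors run from about 1.3 to 11.5 points.
- *Extreme:* p = 0.20, s = 1.00 and e − o = 0.30 give 0.80 × 0.30 = 24 points. This needs every site to be experienced, which Protocol 6.3 does not require.
- *No preference (k = 1):* s = p and the error is zero.

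The sign is arbitrary: if other dermatologists followed the practice more often, the error would run the other way. Enrolling more patients does not reduce it.

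**6. What a breakdown by experience could show.** With 40 sites and 80% experienced, 8 sites are not. A rate of 45% among 8 has a 95% margin of 1.96 × √(0.45 × 0.55 / 8) = 0.34, about ±34 points.

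**The case against.** The strongest reply is that the sentence is soft and serves data quality. It says preferred, not required; Protocol 6.3 expressly admits physicians without experience; and experience can help with data and adverse-event reporting beyond what GCP training provides. That stands as a reason to keep the preference. It does not rescue the random claim, since even a mild preference makes selection unequal unless the probabilities are known and used.

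Second, the preference is not the only feature that limits generalisation. Physicians are invited and may decline (Protocol 6.1), and Protocol 6.2 recommends that half of each site's patients start adalimumab, which shapes the patient mix for objectives ii and v. This also stands. A reader might infer that deleting the sentence in 8.0 would restore valid generalisation; these features show that it would not.

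Third, the scope is narrower than it may look. Protocol 4.0 words its generalisation as being to psoriasis patients. Applying it to dermatologists' practice and to burden is a reading that rests on objectives iii and v. The physician survey in Protocol 10.2 asks for estimates of prevalence, and no table title in the SAP list names a dermatologist joint-screening rate. The practice rates above therefore illustrate a mechanism and do not forecast a planned table.

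**Conclusion.** The contradiction is clear and the justification for generalising does not hold as written. It affects what objectives ii, iii and v may conclude.

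Two stronger readings are tempting. One is that the national estimates are biased, or overstated. The documents do not support this: they give no share of experienced dermatologists, no strength of preference and no difference in practice. The figure of about 10 points, and the span from about 1 to over 20, rest wholly on assumptions, and the direction is unknown. The other is that the primary comparison of adalimumab with topical and traditional systemic agents is compromised. That comparison is made between patients within the study, and nothing in the documents shows that the site preference distorts it.

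**What to change.** **If sites are not yet chosen,** take one of two routes. Remove the preference from Protocol 8.0 and invite dermatologists in random order within region. Or keep the preference for data quality and drop the claim of random selection.

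**If sites are already chosen,** which the July 2015 date of SAP version 3.0 makes likely but does not prove, change the wording only. In Protocol 4.0, 6.0, 6.1 and 6.3 and SAP 2.4 and 2.8, replace the statements of random selection, and the generalisation drawn from them in 4.0, with an account of how sites were actually selected, including the preference. All six places need the change, or the claim survives in one of them.

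**In either case,** record research experience as one yes/no item per site. Report the numbers of dermatologists invited, declining and accepting, by region and by that item. Word the conclusions for objectives ii, iii and v as applying to participating sites. Any split of objective iii by research experience should be labelled descriptive, since few inexperienced sites may be available.

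The cost is wording, one site-level field and a more modest statement of generalisability. Dropping the preference may also slow start-up at untrained sites, although GCP education is already planned for all site personnel.
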